4 LIST OF ABBREVIATIONS

ABBREVIATION	DEFINITION
AE	Adverse event
ALT	Alanine aminotransferase
AST	Aspartate aminotransferase
AUC _{inf}	Area under the concentration-time curve up to infinity
AUC _{last}	Area under the concentration-time curve up to the last measurable time point
AUC τ	Area under the concentration-time curve over a dosing interval
BID	Twice daily
BNP	Brain type natriuretic peptide
C _{max}	Maximum observed blood concentration
CRO	Contract research organization
CR	Complete response
CRF	Case report form
CT	Computed tomography
CTCAE	Common terminology criteria for adverse events
CYP	Cytochrome P450
DCR	Disease control rate
DNA	Deoxyribonucleic acid
ECOG	Eastern Cooperative Oncology Group
ECG	Electrocardiogram
eCRF	Electronic case report form
EDC	Electronic data capture
ENOX2	Ecto-NOX disulfide-thiol exchanger 2
EORTC	European Organization for Research and Treatment of Cancer
ET	Early termination
GCP	Good Clinical Practice
HEENT	Head, ears, eyes, nose, throat
HR	Hazard ratio
HIV	Human immunodeficiency virus
IC ₅₀	Inhibitory concentration of 50%
ICF	Informed consent form
ICH	International Council for Harmonization of Technical Requirements for Pharmaceuticals for Human Use

ABBREVIATION	DEFINITION
IRB	Institutional review board
Kel	Terminal elimination rate constant
LVEF	Left ventricular ejection fraction
MedDRA	Medical Dictionary for Regulatory Activities
MRI	Magnetic resonance imaging
ORR	Objective response rate
OS	Overall survival
P-gp	P glycoprotein
PFS	Progression free survival
PK	Pharmacokinetics
PD	Progressive disease
PR	Partial response
QD	Once daily
QOL	Quality of life
QRS	QRS interval on electrocardiogram
QTc	QT interval corrected for heart rate
QTcF	QT interval corrected for heart rate using Fridericia's formula
RECIST	Response evaluation criteria in solid tumors
RR	Response rate
RT	Radiotherapy
SAE	Serious adverse event
SAP	Statistical analysis plan
SAQ	Suppository Acceptance Questionnaire
SD	Stable disease
SRC	Safety review committee
STS	Soft tissue sarcomas
TEAE	Treatment-emergent adverse event
TID	Three times daily
T _{1/2}	Terminal elimination phase half-life
T _{max}	Time to reach maximum concentration

5 ROLES AND RESPONSIBILITIES

5.1 SPONSOR

Noxopharm Limited (Noxopharm) is responsible for the study design, data collection and management, analysis and interpretation of data, writing of the Clinical Study Report (CSR), and publication of the study results. The study is funded by Noxopharm.

Noxopharm reserves the right to terminate the study at any time. A written explanation will be provided to the Investigator should the study be terminated. Each Investigator is responsible to inform the Institutional Review Board (IRB) of such a decision and to return all study materials to the Sponsor. The Sponsor will also update the status of the study in the Annual Report to FDA.

5.2 INVESTIGATOR AND SITES

The primary roles and responsibilities of all Investigators and other study personnel at all sites are to recruit the appropriate patients for this study, monitor the safety of all the patients and follow the protocol. This study will be conducted in the US and Australia and will take place in academic hospitals or treatment centers.

The sites and Investigators will be paid for their time and use of facilities. There are no conflicts of interest.

5.4 OVERSIGHT COMMITTEE

The Safety Review Committee, (SRC) will include at least one sponsor representative, participating Investigators and may also include a cardiologist or other outside consultants at the Sponsor's discretion. The primary role of the SRC is to assess toxicities, if needed, to determine if they meet the definition of a dose-limiting toxicity (DLT) and make decisions about dose escalation and what dose will be used in the cohort expansion.

6 INTRODUCTION

6.1 BACKGROUND AND RATIONALE

Soft tissue sarcomas (STSs) are mesenchymal neoplasms that can arise from any site within the body, including the extremity, trunk, retroperitoneum, and head and neck. These are biologically heterogeneous diseases, with over 50 subtypes that vary by molecular, histological, and clinical characteristics. The most common subtypes of high-grade STS include

undifferentiated pleomorphic sarcoma, liposarcoma, leiomyosarcoma, synovial sarcoma, and malignant peripheral nerve sheath tumors. Collectively, STSs are rare, accounting for <1% of adult cancers, with an estimated 12,310 new cases in 2016 in the United States (1). Unfortunately, up to 50% of high-risk patients with high-grade STS develop metastases and die from their disease (2). Among the young adult and pediatric population under 20 years of age, STS is one of the top five causes of cancer-related death (1). The median overall survival (OS) for advanced, metastatic STS has historically been in the range of 12 months, while more recent randomized studies have noted survival approximating 18–19 months (3–10). Nonetheless, improvements in the management of high-grade STS are needed.

Anthracyclines (e.g. doxorubicin) remain the standard of care for first-line therapy in high-grade STS, regardless of subtype, presentation and patient characteristics. Anthracyclines intercalate into deoxyribonucleic acid (DNA), thereby blocking DNA and ribonucleic acid synthesis, while also interfering with topoisomerase II, leading to DNA breakage. Doxorubicin has single-agent activity in high grade STS, and demonstrates a dose–response relationship, with doses lower than 60 mg/m² associated with inferior efficacy (11, 12). Because of its toxicity profile however, most dose-intensive treatment schedules administer doxorubicin at 75 mg/m² for otherwise fit patients (13, 14).

In a large multicenter 455-patient study, doxorubicin (75 mg/m²) in combination with an alkylating agent (e.g. ifosfamide), given alone every 3 weeks over 6 cycles showed a higher response rate (RR), 26.5% compared with doxorubicin alone 13.6% (p < 0.0006). The combination also significantly improved progression free survival (PFS) from 4.6 months to 7.4 months [hazard ratio (HR) 0.74, p = 0.003], but there was no significant difference between the two treatments in OS (14.3 months versus 12.8 months, HR 0.83, p = 0.076). Despite its efficacy, there was higher toxicity when using the combination, with 18% of patients receiving doxorubicin plus ifosfamide and 3% of patients receiving doxorubicin alone being unable to complete the planned 6 cycles of therapy due to adverse events (AEs). It should be noted the most common Grade 3–4 toxicities when administering doxorubicin and ifosfamide are related to bone marrow suppression which highlights the need for regular blood-count monitoring, supportive transfusions and growth factor support (14, 15, 16). These findings suggest that combination chemotherapy provides better outcomes for tumor shrinkage, but improvement in OS is lacking, although part of the problem may be overlapping toxicities in the regimens that have been studied.

In a combined Phase 1b/2 study (n=15/133), olaratumab, a platelet-derived growth factor receptor- α blocking antibody in combination with doxorubicin was evaluated for the treatment of anthracycline-naïve STS (17). Patients were treated for up to 8 cycles with the combination doxorubicin and olaratumab and longer with olaratumab alone. Although the median PFS was not significantly improved with olaratumab at 6.6 months compared with 4.1 months for doxorubicin alone, the median OS was 26.5 months with olaratumab, compared with 14.7 months in the doxorubicin alone arm. This almost 1-year difference in OS indicates

that another agent with a different mechanism of action and toxicity profile from doxorubicin may provide improved outcomes in STS, compared to doxorubicin alone.

Idronoxil, a small molecule, acts by binding Ecto-NOX disulfide-thiol exchanger 2 (ENOX2) – a tumor-specific form of external membrane NADH oxidase. As such, the activity of idronoxil is highly specific to tumor cells. Binding of idronoxil to ENOX2 leads to a disruption of the sphingomyelin pathway, preventing the conversion of ceramide to sphingomyelin- 1- phosphate (S1P), and subsequently a cascade of events leading to apoptosis. *In vitro* idronoxil potently sensitizes a broad range of cancer cell lines and adds to the cytotoxic effects of standard chemotherapeutic agents from various classes. In addition, it has been demonstrated that Idronoxil reverses pre-existing resistance (e.g. sensitizes platinum-resistant cells to carboplatin) (18, 19, 20).

In other studies, optimal sensitization with idronoxil occurred with a 24-hour period of idronoxil pre-treatment followed by a 120-hour treatment with a chemotoxin. Several clinical trials have been conducted with idronoxil using intravenous and oral routes of administration. The addition of oral idronoxil [(400 mg three times daily (TID)] to platin based therapy provided no clinical benefit in patients with platinum-resistant ovarian cancer, but there was some evidence of activity in small cell sarcoma or adenocarcinoma of the cervix, vagina or vulva. The high rate of metabolism of oral idronoxil may have led to the failure to show clinical activity in these studies.

To circumvent the high rate of metabolism, a rectal formulation was developed, and one Phase 1 study has been completed in 18 patients with solid tumors. Idronoxil suppository was administered [400 mg once daily (QD) or 400 mg twice daily (BID)] for 14 consecutive days followed by 7 days off treatment. After completion of the NOX66 monotherapy period, carboplatin was added on Day 2 of 7 consecutive days of NOX66 treatment in each cycle. The combination phase of the study consisted of 3 cycles of NOX66 and low-dose carboplatin (AUC=4) followed by three cycles of NOX66 and a higher dose of carboplatin (AUC=6). The patients who completed the monotherapy and all cycles, received NOX66 for a maximum of 56 days and carboplatin for up to 6 cycles. The most common treatment-emergent adverse event (TEAE) by System Organ Class was blood and lymphatic system disorders, with 44% of the patients, half of which experienced mild to severe anemia. In terms of tumor response, at Cycle 6, 1 patient had a partial response (PR), and most had stable disease (SD). Of the 3 deaths in the study, 2 were due to progressive disease and one may have been related to the combination of NOX66 and carboplatin, although an autopsy was not performed.

An ongoing Phase 1 study is evaluating the combination of NOX66 plus palliative doses of radiotherapy (RT) in patients with metastatic castrate resistant prostate cancer who have failed all available treatment. In the first part of the study (dose escalation), 14 patients were treated with either 400, 800 or 1200 mg/day NOX666 (n=4-6/dose) for up to 16 days. Radiotherapy was administered over 8 days and NOX66 treatment began on the day prior to RT and continued until 7 days following completion of RT. In the second part of the study a dose expansion cohort (n=12) with 1200 mg NOX66 is underway.

In 25 patients studied to date, mild (Grade 1) TEAEs of fatigue have been attributed to both NOX66 and radiation, while occurrences of mild dry mouth, oral mucositis, and stomatitis have been considered related to NOX66 alone. Cases of mild radiation dermatitis, oropharyngeal pain, and moderate anaemia and urinary tract infection have been considered related to RT alone.

Three patients in the 800 mg dose cohort died due to disease progression, ≥ 30 days after the last NOX66 dose. Two of these patients experienced severe (Grade 3) TEAEs. One patient developed lymphopenia, and hypocalcemia immediately after completion of treatment, followed one month later by nausea, vomiting, and subsequent death. The other patient developed anaemia after completion of treatment and hypophosphatemia 20 days post treatment completion both of which resolved. Almost three (2.75) months later the patient died. One patient in the 1200 mg dose cohort died due to disease progression ≥ 30 days after the last NOX66 dose. None of these deaths were considered related to NOX66.

The majority of all other TEAEs were mild to moderate (Grades 1-2). Other Grade 3 TEAEs were asthenia, back pain or bone pain, which were reported in 3 patients.

The present study will assess the safety, tolerability, and pharmacokinetics (PK) of NOX66 using a wider range of doses than were tested in the first Phase 1 studies as well a different cytotoxic agent. In addition, preliminary evaluation of the efficacy as well as safety/tolerability and PK for NOX66 will be made in combination with doxorubicin in patients with metastatic STS. Although doxorubicin is used as first line therapy in this disease, median survival is still only about 1 year and there is significant toxicity. Based on nonclinical data as noted in Section 6.2 the effectiveness of doxorubicin could be enhanced in the presence of NOX66.

Additional information on NOX66 may be found in the Investigator's Brochure.

6.2 CHOICE OF COMPARATOR OR CONTROL

The present study is designed to find the maximum tolerated dose (MTD) of the combination of NOX66 with doxorubicin in patients with STS, and therefore no control group or comparator is needed for this study.

All patients will be treated with doxorubicin which is widely held as the initial standard of care for metastatic STS. One week prior to initiation of doxorubicin, patients in the Dose-Escalation Cohorts will also receive 7 days of NOX66 monotherapy which has been shown to be cytotoxic to sarcoma cell lines (n=19) *in vitro* with IC₅₀ values ranging from 0.3 to 18.4 μ M (median 5.2 μ M).

In the Dose Expansion Cohort, all patients will be treated for 1 day with NOX66 (at the MTD of the combination of NOX66 and doxorubicin), before receiving doxorubicin on Day 2 of a 21-day cycle. On Days 2 to 7, NOX66 will be given at the same dose as on Day 1. No therapy is administered from Days 8 to 21 of each treatment cycle.

All patients are eligible to receive up to 6 cycles of doxorubicin.

7 STUDY OBJECTIVES

7.1 PRIMARY OBJECTIVES

- To estimate the maximum tolerated dose (MTD) of NOX66 in combination with doxorubicin
- To characterize the safety and tolerability of NOX66 alone and in combination with doxorubicin.

7.2 SECONDARY OBJECTIVES

- To determine single-and multiple-dose pharmacokinetics (PK) of idronoxil
- To determine the preliminary efficacy and quality of life (QOL) of the MTD of NOX66 in combination with doxorubicin.

7.3 EXPLORATORY OBJECTIVES

- To investigate the relationship between response to NOX66 plus doxorubicin and the following:
 - Dose of NOX66
 - Histopathology (if prior tissue samples/slides are available)
 - Genetic mutations
 - Cytokine/chemokine and ENOX2 dynamics
 - Change in lipid profile from baseline Acceptability of NOX66 dosage form

8 STUDY DESIGN AND OVERALL INVESTIGATIONAL PLAN

8.1 OVERALL INVESTIGATIONAL PLAN

This is a Phase I, open label, dose escalation and dose expansion study of NOX66 given rectally, in cohorts of patients with metastatic STS who have not been exposed to anthracycline therapy, using a fixed dose escalation schema every 21 days to establish the MTD of the combination of NOX66 and doxorubicin.

8.1.1 DOSE-ESCALATION

For all dose escalation cohorts, there will be 7 days of monotherapy treatment with NOX66 followed by a 5- day washout period prior to the start of combination cycles of NOX66 and doxorubicin. The purpose of the monotherapy treatment is to evaluate the safety and tolerability of NOX66 when administered alone and as well as single and multiple dose PK of idronoxil.

The dose-escalation part of the study will include three planned Treatment Groups (800, 1200, 1800 mg daily) of 3 patients each. The first 3 patients will be entered at Dose Level 1 and will receive daily doses of NOX66 for 7 days. All of these doses, except for the 1800 mg have been evaluated in 2 previous clinical trials and have been relatively well tolerated as monotherapy for 14 days and in combination with carboplatin for 42 days.

After a rest period of 5 days and if no significant toxicities (DLT equivalent toxicity) have occurred, patients will enter the combination therapy part of the study which will consist of up to 6 x 21-day treatment cycles. Each cycle will consist of 7 days of NOX66 (at the assigned dose), doxorubicin (75 mg/m²) on Day 2 of the 21-day cycle (administered at approximately 1 hour after rectal application of NOX66) and a rest period of 2 weeks.

For the 800 mg and 1200 mg dose levels NOX66 will be administered twice-daily (BID) with a 400 mg or 600 mg suppository, respectively, and the 1800 mg dose level will entail administration of a 600 mg suppository three times daily (TID). In all cohorts, doxorubicin will be given initially at 75 mg/m² as an intravenous infusion over 15 minutes (or as per standard of care). This dose may be reduced to 60 mg/m², at the Investigator's discretion for unacceptable Grade ≥ 2 toxicity. A dose reduction of 50% is recommended if serum bilirubin is 1.2 -3.0 mg/dL prior to a cycle. If serum bilirubin is 3.1-5.0 mg/dL prior to a cycle, a 75% dose reduction of doxorubicin is recommended.

The MTD of the combination of NOX66 and doxorubicin will be determined over the first 21-day interval (Cycle 1) following monotherapy with NOX66 and in combination of doxorubicin-in 1 of 3 consecutive dose cohorts. The MTD of the combination will either be considered one dose level of NOX66 lower than the dose which produces ≥ 2 DLTs in 3 or 6 patients, depending if a DLT occurred in the first 3 patients, or the highest dose level tested (1800 mg daily) if the aforementioned condition does not occur. A DLT will be defined as a protocol-specified adverse event of toxicity Grade 3-4 (National Cancer Institute Common Terminology Criteria for Adverse Events [NCI-CTCAE] V 5.0) which is considered possibly, probably, or definitely related to the combination of NOX66 and doxorubicin (Section 8.3).

Since this is a multicenter trial, the sites are to notify the Sponsor or designee when a patient has been declared eligible to participate. After 3 patients have completed a 21-day treatment cycle of the combination of NOX66 and doxorubicin and all the safety data are available, assessment of toxicities and decisions about dose escalation and cohort expansion (see below) will be made by the SRC, which will include at least one Sponsor representative participating Investigators, and may also include a cardiologist or other external consultants at the Sponsor's discretion. Recommendations from the SRC could include 1) repeat a dose level, 2) await further safety data if follow-up is pending for patient(s) as determined by the Investigator(s), 3) discontinue the study, 4) escalate the dose to next possible level or 5) take other actions.

Three new patients will be entered at the next dose level of NOX66, if there were no DLTs or only 1 of 6 patients had a DLT at the end of the first cycle.

If no DLT is observed at 1800 mg (Cohort 3), dose escalation will be stopped. The proposed highest dose level (1800 mg) will be declared the MTD, and additional patients will be enrolled, if necessary, to ensure that a total of 6 patients are evaluated at this dose level.

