----------------------	--

level. The previous dose level will then be considered for expansion to 6 patients in order to confirm that it is the MTD level. The MTD is defined as the dose level at which no more than 1 patient out of 6 experienced a DLT up to the end of Cycle 1. If in the first group at 800 mg daily (Cohort 1), 2 or 3 patients develop DLTs, then that dose level is considered to be the DLT level and 3 additional patients need not be tested at that level, but lower doses should be studied.

If no DLT is observed at 1800 mg (Cohort 3), dose escalation will be stopped. The proposed highest dose level (1800 mg) will be declared the MTD, and additional patients will be enrolled, if necessary, to ensure that a total of 6 patients are evaluated at this dose level.

The dose escalation scheme is presented in the following table.

Proposed Starting Dose and Dose Escalation Scheme for NOX66

Cohort	1	2	3
Increment	NA	50%	50%
Total daily dose (mg)	800	1200	1800
Daily regimen (mg)	400 BID	600 BID	600 TID

BID = twice daily, TID = three times daily. For each cohort, safety/tolerability and PK data will be collected on Days 1-2 and 7-8 for respective doses.

Assessment of toxicities and decisions about dose escalation and cohort expansion will be made by a Safety Review Committee, that will include at least one Sponsor representative participating investigators, and may also include a cardiologist or other outside consultants at the Sponsor's discretion.

Assessment of DLTs

Patients who withdraw in Cycle 1 for reasons other than safety or toxicity will be replaced. During the 7-day Monotherapy Period, any patient who develops a significant toxicity, as noted below, will be replaced.

For determination of DLT during Cycle 1, toxicity will be graded using the National Cancer Institute-Common Terminology Criteria for Adverse Events (NCI-CTCAE) Version 5.0. Any of the following, if judged to be associated with NOX66 alone or in combination with doxorubicin (i.e., possibly-, probably-, or definitely related to), will be considered a DLT:

- 1) Grade 3 non-hematological toxicities (excluding alopecia) with the following exceptions:
 - i. Grade 3 nausea/vomiting or diarrhea <72 hours with adequate antiemetic and other supportive care
 - ii. Grade 3 fatigue <1 week
 - iii. Grade 3 electrolyte abnormality that lasts 24 to 72 hours (Investigator's discretion for timeframe), is not clinically complicated

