8.3 DEFINITION AND DETERMINATION OF MTD AND DLT

8.3.1 DEFINITION OF MTD

The MTD is defined as the maximum dose level at which no more than 1 patient out of 6 experienced a DLT at the end of Cycle 1.

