8.3.2 DETERMINATION OF MTD

If at any given dose level, when 1 of 3 patients develops a DLT during Cycle 1, then the dose escalation will halt temporarily, and an additional 3 patients will be recruited at the same dose level. If no further DLTs occur, then dose escalation will resume with the next 3 patients receiving the next higher dose of NOX66. If there are 2 or more patients (out of 6) who

experience DLTs during Cycle 1, dose escalation will be halted, and that level will be declared the DLT dose level. The previous dose level will then be considered for expansion to 6 patients in order to confirm that it is the MTD level. If in the first group at 800 mg, 2 or 3 patients develop DLTs then that dose level is considered to be the DLT level and 3 additional patients need not be tested at that level, but lower doses should be studied.

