15.2.2.3 Safety Pause and Prompt AE Review

If a DLT occurs in 1 patient in a cohort of 3 patients at a given dose level of NOX66 + doxorubicin, then 3 more patients should be enrolled at that same dose level. If a DLT is not observed in the additional 3 patients, the next cohort of 3 new patients may be enrolled at the next higher dose level.

If DLT occurs in 2 patients in a cohort of 6 patients at a given dose level, then this dose level will be defined as the DLT dose level. All Investigators will be informed, no additional patient(s) will be enrolled at the DLT dose level, and dose-escalation will stop. No more than 6 patients should be enrolled at the DLT dose level.

The dose for the next cohort will be determined at the SRC review meeting to evaluate all the available safety (including AEs that are not DLTs).

When a DLT occurs, the site must immediately inform the CRO who will then inform the other sites that a DLT has occurred and evaluate if a second DLT has occurred at any other sites. If 2 or more DLTs occur at the same dose level, further enrollment of new patients at that dose level or higher across all sites will be suspended until the SRC meeting occurs to evaluate if the MTD has been exceeded. To be included in a dose-escalation decision or determination of MTD, an evaluable patient is defined as one who either experienced a DLT during the first 21-day treatment cycle (Cycle 1) or has not experienced a DLT and has taken at least 80% of the prescribed daily doses of NOX66 of the monotherapy period and the first 21-day treatment cycle and completed all safety evaluations required in Cycle 1.

Due to the potential for Cycle 1 discontinuations, patients withdrawing for reasons other than safety will be replaced.

When a dose escalation is stopped, the patients treated at lower doses can continue as planned.

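### Section 8.1.1 names the level below the DLT level as the MTD without a patient number, so a level passed on 0 of 3 could be expanded without being shown to meet the trial's own definition of at most 1 of 6

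*Combined protocol and SAP*

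**What the plan says.** Four places in the combined protocol and SAP bear on how the MTD is fixed.

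- **Section 8.1.1** gives two routes. Under the first: "The MTD of the combination will either be considered one dose level of NOX66 lower than the dose which produces ≥ 2 DLTs in 3" (alternatively six). Under the second, the MTD is 1800 mg daily if that condition never occurs. A level may be passed with no DLT in 3 patients or with 1 of 6. The section requires a total of 6 patients only at 1800 mg with no DLT.
- **Section 8.3.1** defines the MTD as the "maximum dose level at which no more than 1 patient out of 6 experienced a DLT" by the end of Cycle 1.
- **The synopsis** agrees: "The MTD is defined as the dose level at which no more than 1 patient out of 6 experienced a DLT".
- **Section 8.3.2**, with the same wording in the synopsis, describes what follows once a DLT level is found: "The previous dose level will then be considered for expansion to 6 patients in order to confirm that it is the MTD level".

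Section 8.1.2 then enrols 16 patients at the MTD. The Safety Review Committee (SRC) adjudicates the MTD (Section 15.2.1) and decides the expansion dose (Section 5.4). For escalation, Section 15.2.2.2 refers it to the rules in Section 8.1.1.

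**The concern.** Estimating the MTD is the first primary objective, so the rule that produces it should give one answer from one set of data. Here the definition asks for 6 patients, the sentence that assigns the MTD asks for none at the assigned level, and the linking step does not bind. Suppose 1200 mg is passed on 0 of 3 and 1800 mg then shows 2 of 3 patients with a DLT. Section 8.1.1 makes 1200 mg the MTD at once, on 3 patients. Under Section 8.3.1 it is not yet known whether 1200 mg qualifies. At stake is whether 16 patients are treated at a dose that has been checked against the trial's own criterion.

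**Working it through.** **1. The plan's own totals.** The synopsis gives up to about 34 patients, and about 28 if each level uses the minimum.

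- Maximum: 3 levels × 6 = 18; 18 + 16 = 34. Reproduced.
- Minimum, MTD at the top dose: 3 + 3 + 6 = 12; 12 + 16 = 28. Reproduced.
- Minimum with only 3 at the MTD level: 3 + 3 + 3 + 16 = 25. This does not reproduce 28.

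The 28 therefore budgets six patients at the MTD, at least in the top-dose case.

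**2. Which paths are affected.** A level passed on 1 of 6 already satisfies Section 8.3.1. At 1800 mg with no DLT, six are required. What remains is a level passed on 0 of 3 when the next level up becomes the DLT level.

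**3. Chance that such a level would fail at 6.** After 0 of 3, it fails if at least 2 of the next 3 patients have a DLT. With true DLT rate p:

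P(fail) = 3p²(1−p) + p³; P(0 of 3) = (1−p)³; the joint chance is their product.

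The documents give no DLT rate, so every p below is an assumption.

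| p | P(0 of 3) | P(fail at 6, given 0 of 3) | Joint |
|---|---|---|---|
| 0.10 | 0.729 | 0.028 | 0.020 |
| 0.20 | 0.512 | 0.104 | 0.053 |
| 0.25 | 0.422 | 0.156 | 0.066 |
| 0.30 | 0.343 | 0.216 | 0.074 |
| 0.40 | 0.216 | 0.352 | 0.076 |
| 0.50 | 0.125 | 0.500 | 0.063 |

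The joint chance peaks near p = 0.36: 0.64³ × (3 × 0.36² × 0.64 + 0.36³) = 0.262 × 0.295 = 0.077. It stays below 8% at any p.

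**4. How often the MTD would rest on 3 patients.** All escalation paths were enumerated under the Section 8.1.1 sentence alone. Take assumed DLT rates of 0.10, 0.20 and 0.35 at 800, 1200 and 1800 mg. A level is passed on 0 of 3 with probability (1−p)³ and on 1 of 6 with probability 3p(1−p)² × (1−p)³.

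- 800 mg: 0.729 and 0.177, so it fails with 0.094.
- 1200 mg: 0.512 and 0.197, so it fails with 0.291.
- 1800 mg: fails with 0.604.
- MTD below a DLT level, resting on 3: 0.729 × 0.291 + 0.906 × 0.512 × 0.604 = 0.492.
- MTD below a DLT level, resting on 6: 0.177 × 0.291 + 0.906 × 0.197 × 0.604 = 0.159.
- Share resting on 3: 0.492 / (0.492 + 0.159) = 76%. Of these, 7% would fail if extended to 6.

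Over six assumed curves, from (0.05, 0.10, 0.20) to (0.25, 0.35, 0.50), the share resting on 3 runs from 70% to 83%, and 2% to 20% of those would fail at 6.

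**5. Effect on size.** If 1800 mg is the DLT level after 3 patients and 1200 mg was passed on 0 of 3, six at 1200 mg gives 3 + 6 + 3 + 16 = 28. Section 8.1.1 alone gives 3 + 3 + 3 + 16 = 25. Both lie within 34, and the escalation parts (12 and 9) lie within 18.

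**The case against.** The strongest reply is that Section 8.3 is the section devoted to defining and determining the MTD, that its definition applies to every level, and that Section 8.3.2 states the purpose of the extra patients as confirmation. Read together, a level passed on 0 of 3 is a candidate, and Section 8.1.1 is a loose summary that is merely silent on patient number. The budget of 28 points the same way. This stands as evidence of intent. It does not remove the gap, because no sentence makes confirmation mandatory below a DLT level.

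A reader might infer more than the documents support:

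- **That the expanded dose fails the definition, or was never tested.** It would have had no DLT in 3 patients. It has not been shown to meet the criterion, which is a weaker statement.
- **That different sites could reach different MTDs.** Sites do not set the MTD; one SRC does, under a charter to be written before the study starts.
- **That 16% to 35% is the chance of a wrong MTD.** Those figures assume true rates of 25% to 40% and take 0 of 3 as given. The joint chance is below 8%, before also requiring that the next level fails and that the SRC skips confirmation.
- **That counting DLTs instead of patients leads to an over-toxic dose.** Section 8.1.1 counts DLTs, and Section 15.2.2.3 says "If 2 or more DLTs occur at the same dose level, further enrollment of new patients at that dose level or higher across all sites" is suspended, while Section 8.3.2 counts patients ("If there are 2 or more patients (out of 6) who" have DLTs). Read literally, one patient with two DLTs among 3 would trigger the first rule but not the second. This is probably shorthand: Section 8.1.1 itself speaks of 1 of 6 patients, and Section 15.2.2.3 declares the DLT level by patients and uses the event wording only to pause enrolment until the SRC meets. The literal reading also stops escalation earlier, not later.

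**Conclusion.** The conflict is real and lies in the rule for a primary objective. Followed as written, Section 8.1.1 can yield an MTD that rests on 3 patients and has not been shown to meet Section 8.3.1, and 16 patients would then be treated at it. The exposure is limited to levels passed on 0 of 3, and it arises only if Section 8.1.1 is applied alone or the confirmation step is passed over. If that happened, resting on 3 patients would be the usual case for an MTD below a DLT level (70% to 83% over the assumed curves), while the chance that such a level would have failed at 6 is moderate (2% to 20% over the same curves). All of these sizes depend on assumed DLT rates; the contradiction in the text does not. The counting unit is a minor wording point.

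**What to change.** Before any MTD is declared, reconcile the synopsis and Sections 8.1.1, 8.3.1 and 8.3.2 so that a single rule states (a) how many evaluable patients are needed at the level declared the MTD, and (b) whether the confirmation step at the level below the DLT level is mandatory. The other places should refer to that rule, and the SRC charter should carry it. Which rule applies is for the sponsor and investigators to settle. If six is the intent, as the budget and the word confirm suggest, the cost is protocol wording and at most 3 more patients at that level, within the stated maximum of 18 escalation patients.

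In the same edit, align the counting unit in Section 8.1.1 and in the suspension sentence of Section 15.2.2.3 with the patient count used in the synopsis, Section 8.3.2 and the rest of Section 15.2.2.3.
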